### **5.3 Investigative Product Receipt, Labeling and Storage**

All study medications (B2-400 and placebo) will be received, stored, and dispensed by the University of Michigan Health System Research Pharmacy (UH B2D301). Block randomization will be used, as outlined in the statistics section below, and shared with the UMHS Research Pharmacy for proper dispensing of investigational products.

### **5.4 Source**

Study subjects will be recruited from the University of Michigan Department of Dermatology outpatient clinics, and/or local announcement.

### **5.5 Characteristics of Study Group**

Subjects will include up to 50 male or female subjects, 18 years of age or older, of any racial or ethnic background, and in good general health with chronic plaque psoriasis.

#### **5.5.1 Inclusion Criteria**

Subjects must meet all of the following criteria for inclusion in the study:

1. 18 years of age or older

**Title:** The Effect of Riboflavin on Moderate to Severe Plaque Type Psoriasis

**Principal Investigator:** [name]

2. Good general health
3. Willingness and ability to follow the protocol
4. Signed Informed Consent Form, written and witnessed.
5. Stable moderate to severe chronic plaque psoriasis involving 5% or greater total body surface area (TBSA).
6. If subject is a woman of childbearing potential, she must have a negative pregnancy test at screening and agree to use a medically acceptable form of contraception during the screening and throughout the study.

### **5.5.2 Exclusion Criteria**

Patients will be excluded from the study if they meet **any** of the following criteria:

1. Started using a topical steroid stronger than moderate strength, vitamin A or D analog preparations, or anthralin within 14 days of study drug initiation.
2. Initiated a systemic medications, including biologic medication, or phototherapy within 180 days of study drug initiation.
3. Prior or concurrent use of cyclophosphamide.
4. Currently using sulfasalazine therapy.
5. Known hypersensitivity to riboflavin.
6. Enrolled in any other investigational device or investigational drug trial(s) or receipt of any other investigational agent(s) within 28 days of baseline visit.
7. Presence of severe comorbidities such as, diabetes mellitus requiring insulin; CHF of any severity or myocardial infarction or cerebrovascular accident or transient ischemic attack within 3 months of screening visit; unstable angina pectoris, uncontrolled hypertension [sitting systolic BP <80 mm Hg or > 160 or diastolic BP > 100 mm Hg], oxygen-dependent severe pulmonary disease, history of cancer within 5 years [other than resected cutaneous basal or squamous cell carcinoma of the skin or in situ cervical cancer].
8. Any of the following hematologic abnormalities, confirmed by repeat test at least 1 week apart:
  - White blood count <3,000/ $\mu$ L or >14,000/ $\mu$ L
  - Lymphocyte count <1,000/ $\mu$ L

**Title:** The Effect of Riboflavin on Moderate to Severe Plaque Type Psoriasis

**Principal Investigator:** [name]

- Neutrophil count <1,5000/ $\mu$ L
  - Platelet count <150,000/ $\mu$ L
  - Hemoglobin<10 g/dL
9. Liver function test (aspartate aminotransferase [AST], alanine aminotransferase [ALT] or alkaline phosphatase [AlkP]) results that are greater than or equal to 2 times the upper limit of normal (ULN).
  10. Serum creatinine  $\geq$  to 2x the ULN.
  11. Known HIV-positive status or known history of any other immune-suppressing disease.
  12. Any current or past history of psychiatric disease that would interfere with ability to comply with study protocol or give informed consent.
  13. Had grade 3 or 4 adverse events or infections within 28 days before screening, or between screening visit and drug initiation.
  14. Evidence of any skin conditions other than psoriasis that would interfere with the evaluations of the effect of study medication on psoriasis.
  15. Presence of any condition or circumstances judged by the patient's physician, the investigator, or medically qualified study staff to render this clinical trial detrimental or otherwise unsuitable for the patient's participation.
  16. A history of non-compliance with other therapies.
  17. Females who are pregnant, lactating, planning on pregnancy during the study period, or unwilling to use FDA-approved method of birth control.
  18. A history of keloids or excessive scar formation or of healing poorly
  19. A history of allergic reaction to local anesthetics, including lidocaine and epinephrine

## **6 STUDY PROCEDURES**

### **6.1 Screening**

The following are to be performed within 2 weeks prior to admission/Day 0:

1. Obtain written, witnessed informed consent
2. Review inclusion/exclusion criteria

**Title:** The Effect of Riboflavin on Moderate to Severe Plaque Type Psoriasis

**Principal Investigator:** [name]

3. Obtain complete medical history, history of previous psoriasis therapies, concomitant medications, and physical examination
4. For females of childbearing potential, obtain a negative urine pregnancy test.
5. Obtain 9 mL of blood to measure a complete blood count (CBC) and comprehensive metabolic panel (CMP).

## **6.2 Admission/Day 0**

1. Measure vital signs.
2. Review medical history, adverse events and concomitant medications.
3. Skin Exam: Complete PASI, PGA, DLQI, and pruritus assessment using visual analog scale (VAS).
4. Photographs will be taken of significant lesions.
5. Randomize patient
6. For females of childbearing potential, obtain a negative urine pregnancy test.
7. 20 mL of blood will be drawn for measuring plasma levels of riboflavin and FAD.
8. Two psoriatic normal (PN) and two psoriatic plaque (PP) skin samples will be obtained (four total at this visit). These will be performed under local anesthesia (1% lidocaine with epinephrine) using a 6 mm skin punch to obtain skin through to subcutaneous fat. Closures will be made with 4-0 prolene sutures that should be removed in two weeks. Verbal wound care instructions will be provided.
9. Dispense medication.

## **6.3 Return Visits - Weeks 2, 6, 12, 16, 18, 22 and 28**

1. Measure vital signs.
2. Review medical history, adverse events and concomitant medications.
3. Skin Exam: Complete PASI, PGA, DLQI, and pruritus assessment using visual analog scale (VAS).
4. For females of childbearing potential, obtain a negative urine pregnancy test.
5. Photographs will be taken of significant lesions on weeks 0, 12, 16, and 28.

**Title:** The Effect of Riboflavin on Moderate to Severe Plaque Type Psoriasis

**Principal Investigator:** [name]

6. One PP and one PN 6 mm punch biopsy will be performed at week 12. These will be performed as described above. This will be a total of 6 biopsies throughout the study.
7. 20 mL of blood will be drawn for measuring plasma levels of riboflavin and FAD on weeks 2, 12, 18 and 28.
8. 9 mL of blood will be drawn for measuring CBC, CMP on weeks 12 and 28.
9. At week 12 all residual medication will be collected and counted in preparation for patients to cross-over. There will be a four week wash-out period between weeks 12 and 16. At week 16 new medication will be provided and the data from this visit will be used as our new baseline for the second part of the study.
10. At week 28, all residual medication will be collected and counted.

#### **6.4 Closeout Telephone Call at Week 32**

1. Review medical history, adverse events, and concomitant medications.
2. Offer patient an in-office visit for any adverse events identified.

**Title:** The Effect of Riboflavin on Moderate to Severe Plaque Type Psoriasis

**Principal Investigator:** [name]

**Table 1. Time and Events Table**

|   | Screening | Week 0 | Week 2 | Week 6 | Week12 | Week 16 | Week 18 | Week 22 | Week 28 | Week 32
(phone) |
|---|-----------|--------|--------|--------|--------|---------|---------|---------|---------|--------------------|
| Obtain informed Consent                 | X         |        |        |        |        |         |         |         |         |                    |
| Randomization                           |           | X      |        |        |        |         |         |         |         |                    |
| Medical and Psoriatic Treatment History | X         | X      | X      | X      | X      | X       | X       | X       | X       | X                  |
| Physical Exam                           | X         |        |        |        |        |         |         |         |         |                    |
| Con Meds/AE                             | X         | X      | X      | X      | X      | X       | X       | X       | X       | X                  |
| Vital Signs                             |           | X      | X      | X      | X      | X       | X       | X       | X       |                    |
| PASI, PGA                               |           | X      | X      | X      | X      | X       | X       | X       | X       |                    |
| DLQI/ Pruritus VAS                      |           | X      | X      | X      | X      | X       | X       | X       | X       |                    |
| Urine Pregnancy Test for WOCBP          | X         | X      | X      | X      | X      | X       | X       | X       | X       |                    |
| Blood Draw (CBC/CMP)                    | X         |        |        |        | X      |         |         |         | X       |                    |
| Blood Draw (FAD and Riboflavin)         |           | X      | X      |        | X      |         | X       |         | X       |                    |
| Biopsies                                |           | X      |        |        | X      |         |         |         |         |                    |
| Photographs                             |           | X      |        |        | X      | X       |         |         | X       |                    |
| Collect Residual Medication             |           |        |        |        | X      |         |         |         | X       |                    |
| Dispense New Medication                 |           | X      |        |        |        | X       |         |         |         |                    |

**Title:** The Effect of Riboflavin on Moderate to Severe Plaque Type Psoriasis  
**Principal Investigator:** [name]

## **6.5 Premature Withdrawal from Study**

Any subject who experiences adverse effects associated with study participation may be withdrawn from the study. Participation in the study may be discontinued for any of the following reasons:

1. Adverse events
2. Concurrent illness
3. Pain or discomfort during the study
4. Administrative reasons
5. Subject's decision to withdraw consent
6. Protocol violation.

Complete information on all adverse events will be recorded on an Adverse Event Report form (see [Appendix E – Adverse Events LOG](#) for a possible example). The Sponsor-Investigator will review all Adverse Events. The investigator will report adverse events that meet the standard IRBMED reporting guidelines (regarding relatedness and expectedness) to the University of Michigan Institutional Review Board and to the FDA as outlined in 21 CFR 312.32.

## **7 LABORATORY ASSESSMENTS**

Biopsies will be processed for metabolomic profiling and will be taken from psoriatic normal (PN) as well as psoriatic plaque (PP) skin. Six 6 mm punch biopsies of the skin will be performed on each subject throughout the study. Two PN and two PP biopsies will be performed on week 0. Then one PN and one PP biopsy will be performed at week 12. For each subject, we will attempt to obtain all biopsies from the same plaque and the same area of normal skin. These biopsies will be divided in half and used for RNA profiling and histology.

Histological assessment will be performed for all patients using H&E, proliferation markers (Ki67), keratin 16, human beta defensin 2 (hBD2). Samples will be processed in batches of 10 patients at a time to limit batch-to-batch variation. To determine tissue responses, we will run a total of 20 patients for metabolomic and RNA-seq profiling.

All subjects will have a CBC, CMP drawn on screening and then at weeks 12, and 28. All patients in the study will have plasma measurements of riboflavin and FAD at weeks 0, 2, 12, 18, and 28. This will be a total of approximately 127 mL of whole blood per subject.

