### 4 STUDY DESIGN

A 28-week, double-blind, placebo-controlled, prospective study with cross-over of both the riboflavin and placebo groups at the 12-week time mark.

Patients will take either 400 mg of riboflavin (“B2-400”) or a placebo by mouth once a day for 12 weeks. There will be a four week wash-out period at week 12 as the groups cross-over.

We propose using a 400 mg daily dose in this clinical trial as there is the most evidence in previous human studies for a clinical effect with this dose. While data suggesting equivalent activity of riboflavin at a lower dose is intriguing, we feel it is premature to choose a lower dose based off the findings in one trial that was stopped prematurely.

Up to 50 subjects will be enrolled. Six skin biopsies will be performed to measure metabolomics profiles, and there will be five blood draws to measure serologic markers.

**Title:** The Effect of Riboflavin on Moderate to Severe Plaque Type Psoriasis  
**Principal Investigator:** [name]

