## **11 STATISTICAL METHODS**

A block randomization schedule will be created and all subjects randomly assigned to a sequence of treatment and dispensed study product. Assuming a large effect size and a conservative amount of correlation between the measurements, a sample size of 22 subjects in each sequence yields a statistical power of 80%.

All clinical and laboratory assessments will be descriptively summarized at each visit (weeks 0, 2, 12, 16, 18, and 28) for the modified intent-to-treat population. Continuous variables will be summarized with standard descriptive statistics including mean, standard deviation and range. Categorical variables will be summarized by frequency and percentage (N, %).

Differences within each sequence of treatment from baseline to endpoint will be assessed using parametric general linear models such as the paired t-test. The two sequences will also be compared with respect to dichotomized improvement from baseline to the 12-week visit for key clinical endpoints using the McNemar test. Assuming no carryover effects due to the four-week washout period, all data will be pooled and used to estimate the treatment effect. An analysis testing the assumption of equal carryover effects will be performed. Wilcoxon signed rank test will be used to compare ordinal or nominal assessments. Parametric t-tests will be used to determine if continuous laboratory assessments are significantly different between the treatment groups.

**Title:** The Effect of Riboflavin on Moderate to Severe Plaque Type Psoriasis  
**Principal Investigator:** [name]

An overall alpha-level of 0.05 will be used to determine statistical significance and all statistical tests will be two-sided. All data will be analyzed using SAS (SAS Institute, Inc., Version 9.3) software.

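### Tissue is biopsied only in period 1, so its analysis is a parallel week-12 comparison: Section 11 should say so, adjust for the week-0 tissue values, and balance the 20 profiled patients by sequence

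*Combined protocol and SAP*

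**What the plan says.** All references are to the combined protocol and SAP.

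- **Design (Section 4).** Two 12-week periods with a switch between them: "There will be a four week wash-out period at week 12 as the groups cross-over". Period 2 runs from week 16 to week 28.
- **Biopsies (Sections 6.2, 6.3 and 7, Table 1).** Section 7 gives the total, "Six 6 mm punch biopsies of the skin will be performed on each subject throughout the study", and the schedule: "Two PN and two PP biopsies will be performed on week 0", followed by "Then one PN and one PP biopsy will be performed at week 12". Section 6.3 agrees ("One PP and one PN 6 mm punch biopsy will be performed at week 12") and closes the count: "This will be a total of 6 biopsies throughout the study". Table 1 marks biopsies at weeks 0 and 12 only.
- **Who is assayed (Section 7).** Histology (H&E, Ki67, keratin 16, hBD2) is done in every patient. The profiling subset is smaller: "To determine tissue responses, we will run a total of 20 patients for metabolomic and RNA-seq profiling". How those 20 are chosen, and how they divide between sequences, is not stated.
- **Analysis (Section 11).** If there is no carryover, "all data will be pooled and used to estimate the treatment effect". Continuous laboratory measures are compared between treatment groups by t-test. Nothing is said about tissue being limited to period 1, or about how the two week-0 samples are used.
- **Endpoints (Sections 3.1 and 3.2).** PASI, PGA, pruritus, DLQI and plasma riboflavin/FAD. No tissue measure is listed.

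**The concern.** The clinical scores and plasma riboflavin/FAD are measured at the end of both periods, so each completer supplies a riboflavin value and a placebo value. Tissue does not work that way. Placebo-first patients are biopsied untreated and on placebo, and take riboflavin only when no tissue is collected. Riboflavin-first patients are never biopsied on placebo. No one supplies a within-person tissue difference between treatments, so a pooling rule that covers all data has nothing to pool for tissue.

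What remains is a comparison between different people at week 12, with 20 patients for the most expensive assays. In that setting the week-0 tissue values are the main source of extra precision, and they are already being collected. A plain t-test on week-12 values leaves them unused. The sequence split of the 20 is also left open, although it fixes how many profiled patients have an on-riboflavin sample. Because the Background motivates the trial by a tissue finding, the precision of the tissue analysis matters even though it is not a formal endpoint.

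**Working it through.** **1. Reproduce the plan's count.** Week 0: 2 normal + 2 plaque = 4. Week 12: 1 + 1 = 2. Total 4 + 2 = 6, as stated. Period 1 holds all six; period 2 holds none.

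**2. Inputs.** From the documents: 20 profiled patients (Section 7); 22 per sequence as the planned size (Section 11), used for histology; two-sided alpha 0.05 (Section 11). Assumed, because the documents give no figures: a 10:10 split of the 20, an effect of 0.8 SD, a between-visit correlation ρ of 0.3/0.5/0.7, and the same ρ between the two week-0 samples.

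**3. Variance of the between-sequence difference (SD units, n per sequence).**
- Unadjusted t-test at week 12: 2/n.
- ANCOVA, one week-0 sample: (2/n)(1 − ρ²).
- ANCOVA, mean of two week-0 samples: (2/n)(1 − 2ρ²/(1 + ρ)).

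**4. Profiled subset, n = 10.** Power is from the noncentral t with noncentrality 0.8/SE, on 18 df (unadjusted) or 17 df (ANCOVA).

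| Analysis | Variance at ρ = 0.3/0.5/0.7 | SE | Power |
|---|---|---|---|
| Unadjusted | 0.200 at any ρ | 0.447 | 0.40 |
| One baseline | 0.182/0.150/0.102 | 0.427/0.387/0.319 | 0.42/0.50/0.66 |
| Mean of two | 0.172/0.133/0.085 | 0.415/0.365/0.291 | 0.44/0.54/0.74 |

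**5. Histology, n = 22** (42 or 41 df).

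| Analysis | Variance at ρ = 0.3/0.5/0.7 | Power |
|---|---|---|
| Unadjusted | 0.0909 at any ρ | 0.74 |
| One baseline | 0.0827/0.0682/0.0464 | 0.78/0.85/0.95 |
| Mean of two | 0.0783/0.0606/0.0385 | 0.80/0.89/0.98 |

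**6. How firm the gains are.**
- If the two week-0 samples correlate more strongly with each other than with week 12, the gain from the second sample shrinks. If they correlate perfectly it vanishes, so the truth then lies between the last two rows of each table.
- The formulas ignore the cost of estimating the slope, which multiplies the variance by about 1 + 1/(2n − 4). For n = 10 that is 1 + 1/16 = 1.06, and it lowers the ANCOVA powers in step 4 by 0.02 to 0.03. At ρ = 0.3 with one baseline this removes most of the gain; at 0.5 and 0.7 a clear gain remains.
- A t-test on change from week 0 would not substitute. Its variance is (2/n) × 2(1 − ρ) = 0.28/0.20/0.12 for n = 10, larger than ANCOVA at each ρ.

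**7. Sequence split of the 20.** If the 20 were a simple random draw from 44 (22 per sequence), a split of 7/13 or worse has hypergeometric probability 0.13. Its cost is (1/7 + 1/13)/(2/10) = 0.2198/0.2 = 1.10, about 10% more variance.

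**8. For comparison, within-subject contrasts.** With one pair of samples at each of weeks 0, 12 and 28 (2 + 2 + 2 = 6), the crossover variance for 20 patients is 2(1 − ρ)/20 = 0.07/0.05/0.03, and power is 0.82/0.92/0.99.

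**The case against.** The strongest reply is that the week-12 comparison is randomised, concurrent and free of carryover, so nothing is wrong with it. That stands. A reader might infer from the missing period-2 tissue that the tissue comparison is biased or unusable; the documents do not support that, because both sequences are biopsied on the same schedule.

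A second reply is that Section 11 already has a rule for laboratory data, and a between-group t-test fits a week-12 tissue comparison. This stands in part. The rule can be applied, but it does not use the week-0 values, and the pooling sentence does not exempt tissue. The paired tests within each sequence do use week 0, but they do not compare riboflavin with placebo.

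Third, the power loss is easily overstated. One might read all tissue work as resting on 10 against 10 patients; Section 7 limits only metabolomics and RNA-seq to 20. Nor is a lopsided split of the 20 established. The 0.13 in step 7 assumes a simple random draw, whereas Section 11 uses block randomisation and Section 7 processes samples in batches of 10. Profiling consecutive enrollees would keep the split near even, and a 7/13 split costs only about 10% in variance.

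Fourth, it is tempting to call the second week-0 pair spare and to treat its absence from week 28 as a mistake. No purpose is stated for it, but that does not show that it has none. Moving it would lose the duplicate baseline, leave no week-16 tissue baseline and make the contrast depend on no tissue carryover across a four-week washout. It may also add a third assay time point and a suture-removal visit, since the contact after week 28 is a telephone call. The schedule is a defensible trade-off.

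**Conclusion.** The point holds as one of precision and specification. As scheduled, tissue response is a period-1 parallel comparison that lies outside the pooled crossover estimate, and Section 11 neither says so nor uses the week-0 tissue values. Under the stated assumptions, adjustment adds roughly 0.02 to 0.34 to power for the profiled markers (0.40 to between 0.42 and 0.74) and 0.04 to 0.24 for histology (0.74 to between 0.78 and 0.98). The gain is small at ρ = 0.3 and substantial at 0.7. The effect size, the correlations and the 10:10 split are assumptions; the sampling schedule and the numbers assayed come from the documents.

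A reader might go further and conclude that the trial's efficacy result is weakened. It is not: tissue is not a listed primary or secondary endpoint, and PASI, the other clinical scores and plasma levels are measured in both periods.

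**What to change.** **Section 11.** State that tissue outcomes are outside the pooled crossover estimate. Compare week-12 values between sequences by ANCOVA adjusted for the week-0 value of the same skin type, using the mean of the two week-0 samples where both are assayed.

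**Section 7.** State that the research pharmacy, which holds the randomisation schedule under Section 5.3, selects the 20 profiled patients as 10 per sequence and releases only the subject identifiers, so that the study team and laboratory stay blinded.

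Cost: SAP wording and one instruction to the pharmacy, with no additional biopsies or assays.

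**Optional, for the sponsor to weigh.** State what the second week-0 pair is for. If it has no separate purpose, moving it to week 28 keeps six biopsies and gives the within-subject contrasts of step 8. That needs a protocol and consent amendment and carries the drawbacks set out in the last paragraph of the objection. The Section 11 and Section 7 changes above are worth making if the schedule stays as it is.
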